3.6.3 Anti-RSV neutralizing antibody

For each season as well as the two consecutive seasons (ie, Season 1, Season 2, Season 1 + Season 2) the following summaries will be provided using the respective as-treated population. The Season 1 summaries will also be repeated for each cohort (pre-term, CHD/CLD).

Individual MEDI8897 and palivizumab serum RSV neutralizing antibody levels will be tabulated by treatment group along with descriptive statistics. RSV neutralizing antibody levels in serum will be summarized by geometric mean concentration and geometric meanfold rise and corresponding 95% CI for each treatment group at each visit. RSV neutralizing antibody level $t_{1/2}$ will be estimated using non-compartmental analysis, if data permit and may be reported outside the CSR.

Box plots of RSV neutralizing antibody levels in logarithm scale with base 10 will be provided by treatment group and by visit for each season.

3.6.4 RSV serology

For each season as well as the two consecutive seasons (ie, Season 1, Season 2, Season 1 + Season 2) the following summaries will be provided using the respective as-treated population. The Season 1 summaries will also be repeated for each cohort (pre-term, CHD/CLD).

RSV seroresponses will be evaluated as a measure of "RSV exposure" in the MEDI8897 and palivizumab groups. Analysis of serum antibody levels to RSV antigens in MEDI8897 and palivizumab recipients will be summarized by geometric mean concentration and geometric mean-fold rise from baseline and corresponding 95% CI for each treatment group at each visit. Seroresponses in MEDI8897 recipients will be determined by examining the fold-rise in antibodies to Post-F, Ga, Gb, and N antigens; seroresponses in palivizumab recipients will be determined by examining the fold-rise in antibodies to Ga, Gb, and N antigens. By measuring antibodies to Post-F, Ga, Gb, and N for MEDI8897 recipient, and measuring antibodies to Ga,

Gb and N for palivizumab recipient: 1) baseline maternal antibodies and their decay can be measured over time; 2) the exposure to RSV (infection) that results in an increase in RSV-specific Abs for the infant's own immune system can be determined. In addition, number and percentage of subjects with RSV exposure (defined as ≥ 4-fold rise in serum antibody levels to any RSV antigen from the previous timepoint) will be summarized. A subject shows "evidence of exposure" if this criterion is met for any set of consecutive timepoints. The summary will be provided by treatment group at scheduled visits when the serum samples were collected. The summary will be cumulative; that is, if subjects show exposure in a previous timepoint, they should be included in later timepoints as well. At each scheduled timepoint, the denominator will be the number of subjects with a result.

Box plots of serum antibody levels to RSV antigens in logarithm scale with base 10 will be provided by treatment group and by visit for each season.

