4.8.6.2 RSV Serology

Analysis of anti-RSV antigens antibody levels in serum in MEDI8897 and palivizumab recipients will be summarized by geometric mean titer and geometric mean-fold rise and corresponding 95% CI for each treatment group at each visit. Seroresponses in MEDI8897 and palivizumab recipients will be determined by examining the fold-rise in antibodies to Ga, Gb, and N antigens.

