- Added section 3.5.1.3 Sensitivity Analyses of incidence of medically attended LRTI due to RT-PCR-confirmed RSV to evaluate the impact of wrong treatment, missing and out-ofwindow active doses on the primary efficacy endpoint analysis
- In section 3.5.3, the summary of subjects with at least one medically attended LRTI will be broken down by RSV status only. Clarified rules to define severity among multiple medically attended LRTIs, and among multiple hospitalizations due to any respiratory illness, separately.
- In section 3.6.1, removed HUR summaries for Season 1 + Season 2; removed HRU summaries for the following medically attended LRTI categories: non-RSV LRTI (protocol defined), RSV LRTI (non-protocol defined), non-RSV LRTI (non-protocol defined); added analyses on pre-specified OTC medications (analgesics/antipyretics), prescribed medications

(systemic antibacterial agents), and anti-wheezing medications; removed original analyses on overall prescriptions or OTC medications

- In section 3.6.2, removed caregiver burden summaries for Season 1 + Season 2; removed caregiver burden summaries for the following medically attended LRTI categories: non-RSV LRTI (protocol defined), RSV LRTI (non-protocol defined), non-RSV LRTI (non-protocol defined).
- In section 3.6.3 and section 3.6.4, added box plot for serum antibody levels for all subjects by treatment group and by visit
- In section 3.6.4, added summary of RSV exposure (≥ 4-fold rise in serum antibody levels to any RSV antigen from the previous timepoint); added Post-F antigen for seroresponses in MEDI8897
- In section 3.6.5, updated the scope of genotypic and phenotypic analyses, which will be detailed in a separate virology plan
- In section 3.7, added definition of treatment-emergent AEs for each reporting periodIn section 3.7, clarified the scope of safety summaries for Season 1 + Season 2: Season 1 + Season 2 safety summary would provide 2-year incidence of AE. Considering the potential bias of directly comparing MEDI8897/MEDI8897 with Palivizumab/Palivizumab, only several key safety summaries will be repeated for Season 1 + Season 2.
- In section 3.7.1, updated the definition for non-treatment emergent AE/SAE and clarified that pre-planned surgeries that occur during the study for CHD subjects are a part of nontreatment emergent AE/SAE

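### RSV exposure percentages in SAP 3.6.4 are not like-for-like between arms (four antigens against three), and a cumulative count is divided by a visit-specific denominator

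*SAP*

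**What the plan says.** SAP 3.6.4 (RSV serology) sets the antigens by product in one sentence. It begins "Seroresponses in MEDI8897 recipients will be determined by examining the fold-rise in antibodies to Post-F, Ga, Gb, and N antigens; seroresponses in palivizumab recipients", and its second half reads in full: "seroresponses in palivizumab recipients will be determined by examining the fold-rise in antibodies to Ga, Gb, and N antigens". Protocol 4.8.6.2 gives a single list: "Seroresponses in MEDI8897 and palivizumab recipients will be determined by examining the fold-rise in antibodies to Ga, Gb, and N antigens". The SAP amendment history for version 2.0 records the change, "added Post-F antigen for seroresponses in MEDI8897", without a reason. Section 3.6.4 explains what the antibody measurements are for, but not why the lists differ.

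Exposure is then "defined as ≥ 4-fold rise in serum antibody levels to any RSV antigen from the previous timepoint", tabulated by treatment group at each sampling visit. The count accumulates: "if subjects show exposure in a previous timepoint, they should be included in later timepoints as well". The denominator does not: "At each scheduled timepoint, the denominator will be the number of subjects with a result".

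The SAP leaves three things open: whether the any-antigen criterion follows the arm-specific lists, which list applies to the palivizumab/MEDI8897 group in Season 2, and whether a child exposed earlier but without a current result belongs in the denominator.

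**The concern.** Under an any-antigen rule, a longer list gives more chances to be positive, through a true response or a chance 4-fold rise. If the rule follows the arm-specific lists, MEDI8897 recipients get one more chance in every interval between samples. Part of any difference between the two exposure columns would then come from the definition.

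The second problem is arithmetic. A child who seroresponded by Day 151 and gave no Day 361 sample stays in the Day 361 numerator but, read literally, leaves the denominator. The percentage then rises with missing samples, and nothing caps it at 100%. SAP 3.10 expects the pandemic to disrupt blood collection, so missing samples are not hypothetical. Two of the Season 2 groups have only about 50 children each, where a few missing samples move the figure.

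What is at stake is the accuracy of an exploratory table. Both documents warn that RSV event rates may be much lower than assumed, so readers may turn to serological exposure as background for the LRTI rates. That use is an inference; neither document plans it.

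**Working it through.** **The plan's own figures.** Neither document states a figure for the exposure table. The arm sizes used below (600 and 300) are from Protocol 4.8.2, whose sizing statement reproduces: 1 − 0.995^600 = 0.951, against the stated 95%.

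**Inputs from the documents.** Number of antigens m = 4 (MEDI8897) or 3 (palivizumab), SAP 3.6.4. Intervals between consecutive samples K = 3 in Season 1: baseline to Day 31, Day 31 to 151, Day 151 to 361 (Protocol Figure 1 and Table 5).

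**Assumptions, not in the documents.** True exposure π of 20% to 60%, the same in both arms; per-antigen sensitivity s of 50% to 90%; per-antigen, per-interval false-rise rate f of 0 to 2%; independent antigens; one exposure interval per exposed child.

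**Step 1: four antigens against three.**

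- Exposed child called exposed: 1 − (1 − s)^m × (1 − f)^(m(K − 1))
- Never-exposed child called exposed: 1 − (1 − f)^(mK)
- Arm rate: π × first + (1 − π) × second

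With π = 0.4, s = 0.7, f = 0.01:

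- m = 4: 1 − 0.3^4 × 0.99^8 = 0.9925; 1 − 0.99^12 = 0.1136; rate = 0.4 × 0.9925 + 0.6 × 0.1136 = 46.5%
- m = 3: 1 − 0.3^3 × 0.99^6 = 0.9746; 1 − 0.99^9 = 0.0865; rate = 0.4 × 0.9746 + 0.6 × 0.0865 = 44.2%

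The gap is 2.3 points with no true difference. Selected results, including the smallest and largest gaps over the assumed range:

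| π | s | f | Four antigens | Three antigens | Gap (points) |
|---|---|---|---|---|---|
| 20% | 90% | 0 | 20.0% | 20.0% | 0.0 |
| 40% | 70% | 1% | 46.5% | 44.2% | 2.3 |
| 20% | 50% | 2% | 36.2% | 31.1% | 5.1 |
| 60% | 50% | 2% | 65.4% | 60.0% | 5.4 |

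Among never-exposed children alone, f = 1% gives 11.4% (12 looks) against 8.6% (9 looks). SAP Appendix 2 shows no Day 31 sample under the EU protocol. There K = 2, and the same comparison is 1 − 0.99^8 = 7.7% against 1 − 0.99^6 = 5.9%. If the antigens always rose together, a fourth would add nothing and the gap would be 0. With Ga, Gb and N in both arms the gap is 0 by construction.

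**Step 2: cumulative count over children with a current result.** Let q be the proportion with no result at the visit. Assume it is unrelated to exposure and that all exposures were detected at earlier visits. The literal rule gives πN / ((1 − q)N) = π / (1 − q).

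| True cumulative exposure | q = 5% | q = 10% | q = 20% |
|---|---|---|---|
| 20% | 21.1% | 22.2% | 25.0% |
| 40% | 42.1% | 44.4% | 50.0% |
| 60% | 63.2% | 66.7% | 75.0% |

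- Equal missingness, π = 40%, q = 10%: 240/540 = 44.4% and 120/270 = 44.4%. Both arms are inflated and there is no gap between them.
- Unequal missingness, π = 40%: 5% missing on MEDI8897 gives 240/570 = 42.1%; 20% missing on palivizumab gives 120/240 = 50.0%.
- Alternative reading, with numerator and denominator both limited to children with a current result: at q = 10%, 0.9 × 240 = 216, and 216/540 = 40.0%. There is no inflation.

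**The case against.** The strongest reply is that this is an exploratory table with no planned test or contrast. The objective speaks of evaluating exposure in both groups, whereas neighbouring exploratory objectives speak of comparison. Section 3.6.4 also gives geometric means and fold-rises by arm and visit. This stands, and it limits the importance of the point. It does not settle it: the SAP disclaims comparison for ADA (3.8) and for Season 2 efficacy in the MEDI8897/MEDI8897 group (3.5.1.2), but has no such caveat here and sets exposure out by treatment group.

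The Post-F addition was deliberate, and F already appears in the protocol's serology endpoint (Table 3). Protocol 1.2 says the two antibodies bind F at distinct sites, so there may be a sound assay reason to use Post-F in one arm only. Neither document makes that link. If the reason exists, Ga, Gb and N is the like-for-like set, which supports the fix.

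The denominator wording can be read to restrict both counts, and table specifications are left to a programming plan. The visit windows in SAP Appendix 2 allocate every collected sample, which limits empty cells. These points are fair, but the SAP does not state the restrictive reading and its literal wording gives the wrong percentage.

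A reader might also infer a spurious difference of 6 to 10 points. That is the gap in detection among infected children only, with assumed independent sensitivities of 0.2, 0.3 or 0.5: 59.0% against 48.8%, 76.0% against 65.7%, and 93.8% against 87.5%. At 20% true exposure the arm rates would differ by 0.2 times those gaps, or 1.3 to 2.1 points before false rises.

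**Conclusion.** The point holds as a defect of definition in an exploratory table. On the arm-specific reading, the exposure percentages are not like-for-like, and the direction favours a higher reading on MEDI8897, by about 0 to 5 points at equal true exposure. That size depends wholly on the assumed values and on independence; correlated responses bring it towards 0. The denominator rule, read literally, overstates cumulative exposure in each arm, and creates a difference between arms only if missingness differs. Nothing in the documents indicates that it will.

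Two stronger conclusions are tempting and not supported. One is that exposure cannot be compared between arms: Ga, Gb and N are measured in both, so a like-for-like rate needs no new data. The other is that the table will make MEDI8897 look more protective: no analysis adjusts or stratifies LRTI by serological exposure, and the efficacy endpoint rests on central RT-PCR and clinical criteria. The change is worth making because it is cheap and removes an unexplained departure from the protocol.

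**What to change.** Amend SAP 3.6.4 as follows.

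- Define exposure as a 4-fold or greater rise to Ga, Gb or N in every treatment group, naming palivizumab/MEDI8897 in Season 2 explicitly.
- Report Post-F for MEDI8897 recipients as a separate supportive row, and state why it is used in that arm only.
- Set the cumulative denominator to children with at least one evaluable pair of consecutive samples up to that visit, so that every child in the numerator is in it. Show the number with a result at the visit alongside.

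The cost is SAP wording and one extra row; no new samples or assays are needed. Detection in the MEDI8897 arm will be slightly lower in the common-antigen row. The new denominator also keeps children who later stopped giving samples, so exposures in their unsampled intervals go uncounted; the count of current results lets the reader judge this.

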4.1.3 Exclusion Criteria

Any of the following would exclude the subject from participation in the study:

- 1 Any fever ($\geq 100.4^{\circ}\text{F}$ [$\geq 38.0^{\circ}\text{C}$], regardless of route) or acute illness within 7 days prior to randomization
- 2 Any history of LRTI or active LRTI prior to, or at the time of, randomization
- 3 Known history of RSV infection or active RSV infection prior to, or at the time of, randomization

- 4 Hospitalization at the time of randomization, unless discharge is expected within the 7 days after randomization
- 5 Requirement for mechanical ventilation, extracorporeal membrane oxygenation, CPAP, or other mechanical respiratory or cardiac support at the time of randomization
- 6 Anticipated cardiac surgery within 2 weeks after randomization
- 7 Anticipated survival of < 6 months after randomization
- 8 Receipt of any investigational drug
- 9 Known renal impairment
- 10 Known hepatic dysfunction including known or suspected active or chronic hepatitis infection
- 11 Clinically significant congenital anomaly of the respiratory tract
- 12 Chronic seizure, or evolving or unstable neurologic disorder
- 13 Prior history of a suspected or actual acute life-threatening event
- 14 Known immunodeficiency, including human immunodeficiency virus (HIV)
- 15 Mother with HIV infection (unless the child has been proven to be not infected)
- 16 Any known allergy, including to immunoglobulin products, or history of allergic reaction
- 17 Receipt of palivizumab or other RSV mAb or any RSV vaccine, including maternal RSV vaccination
- 18 Receipt of any monoclonal or polyclonal antibody (for example, hepatitis B immune globulin, intravenous immunoglobulin) or anticipated use during the study
- 19 Any condition that, in the opinion of the investigator, would interfere with evaluation of the study drug or interpretation of subject safety or study results
- 20 Concurrent enrollment in another interventional study
- 21 Children of employees of the sponsor, clinical study site, or any other individuals involved with the conduct of the study, or immediate family members of such individuals

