4.1.6 Discontinuation of Investigational Product

An individual subject will not receive additional doses of study drug, including continued dosing in Season 2 for subjects with CLD/CHD, if any of the following occur in the subject in question:

- 1 Withdrawal of consent
- 2 Hypersensitivity reaction assessed as related to study drug

Subjects who have received any study drug will be followed for protocol-specified assessments including follow-up of any AEs unless consent is withdrawn specifically from further study participation (Section 4.1.5) or the subject is lost to follow-up. Subjects who have not received study drug, regardless of reason, will not be followed.

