4.7.1 Permitted Concomitant Medications

Investigators may prescribe concomitant medications or treatments deemed necessary to provide adequate supportive care including routine vitamins and iron. Specifically, subjects should receive full supportive care during the study, including transfusions of blood and blood products, and treatment with antibiotics, anti-emetics, anti-diarrheals, and analgesics, and other care as deemed appropriate, and in accordance with their institutional guidelines.

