4.7.2 Prohibited Concomitant Medications

Use of concomitant medications including over-the-counter medications (except for routine vitamins and iron), herbal supplements, etc from Day 1 through Day 15 post dose is discouraged. Subject's legal representative must be instructed not to administer any medications, including over-the-counter products, without first consulting with the investigator.

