3.2 Analysis Populations

The analysis populations are defined in Table 1.

Table 1Analysis Populations

Population	Description	
Intent-to-treat (ITT)	The ITT population (Season 1) includes all subjects randomized in Season 1. In this population, subjects will be analyzed according to their randomized treatment group in Season 1.	
population (Season 1)	The analysis for baseline/demographic characteristics, efficacy and HRU for Season 1 will be performed on this population.	
Intent-to-treat (ITT)	The ITT population (Season 2) includes all CHD/CLD subjects enrolled in Season 2. In this population, subjects will be analyzed according to their randomized treatment group through the two seasons (ie, in Season 1 and in Season 2).	
population (Season 2)	The analysis for baseline/demographic characteristics, efficacy, and HRU for Season 2 and/or through the two seasons (Season 1 + Season 2), will be performed on this population.	
	The As-treated population (Season 1) includes subjects who receive any investigational product in Season 1. In this population, subjects will be analyzed according to the actual treatment received in Season 1.	
	The analysis for safety, PK, ADA, serology, and RSV neutralizing antibody for Season 1 will be performed on this population.	
As-treated population	For subjects who accidentally receive both MEDI8897 and palivizumab in Season 1:	
(Season 1)	- For summaries on safety, subjects who receive any amount of MEDI8897 will be included in the MEDI8897 group.	
	 For summaries on PK, ADA, serology, and RSV neutralizing antibody, subjects will be analyzed according to the first dose they receive. The data collected up to the point of dose switch will be included in the summaries. All the data collected afterwards will be presented in the listing. 	
	The As-treated population (Season 2) includes subjects who receive any study investigational product in Season 2. In this population, subjects will be analyzed according to the actual treatment received through the two seasons (ie, in Season 1 and in Season 2).	
As-treated population (Season 2)	The analysis for safety, PK, ADA, serology, and RSV neutralizing antibody for Season 2 and/or through the two seasons (Season 1 + Season 2), will be performed on this population.	
	For subjects who received mixed doses of investigational product, similar rules as described above for Season 1 will be applied for Season 2.	

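### The SAP's RSV-exposure rule makes no exception for passively received antibody, so donor antibody can be scored as infection in the exploratory serology tables

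*SAP*

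**What the plan says.** **Entry.** Exclusion 18 in Protocol 4.1.3 covers "Receipt of any monoclonal or polyclonal antibody (for example, hepatitis B immune globulin, intravenous immunoglobulin) or anticipated use during the study". Exclusion 17 covers "Receipt of palivizumab or other RSV mAb or any RSV vaccine, including maternal RSV vaccination". Both are eligibility criteria.

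**After randomization.** Protocol 4.7.1 says that "subjects should receive full supportive care during the study, including transfusions of blood and blood products". Protocol 4.7.2 is headed as a list of prohibited medication but names no antibody product; it says that use of concomitant medication "from Day 1 through Day 15 post dose is discouraged". Receipt of non-study antibody is not among the reasons in Protocol 4.1.6 for stopping study drug.

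**Serology.** SAP 3.6.4 measures antibody to Post-F, Ga, Gb and N in MEDI8897 recipients, and to Ga, Gb and N in palivizumab recipients. It gives two purposes: to follow the decay of maternal antibody, and to detect infection through the infant's own antibody response. The exposure criterion is a "fold rise in serum antibody levels to any RSV antigen from the previous timepoint" of at least 4. A subject who meets it once is counted at all later timepoints. Season 1 tables are repeated for the preterm and CLD/CHD cohorts.

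**Data cut-off.** SAP 3.2, Table 1, deals with infants who accidentally receive both study products. For PK, ADA, serology and neutralizing antibody, "The data collected up to the point of dose switch will be included in the summaries"; later data are only listed. Nothing comparable exists for non-study antibody.

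**The concern.** The criterion does not match its aim. It responds to any rise in circulating RSV antibody, whereas the aim is to identify antibody produced after infection. Pooled immunoglobulin or plasma from adult donors can produce such a rise without infection. That donor products carry RSV antibody is an inference, but the documents support it: SAP 3.6.4 expects mothers to pass RSV antibody to their infants, and Protocol 1.1 says that 90% of children are infected within their first two years.

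The route is foreseeable. At least 100 infants with hemodynamically significant CHD are planned, and Protocol 3.1.2.3 has its own rules for cardiopulmonary bypass during the dosing period. Transfusion is permitted in all infants.

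Two results are at stake: the exposure percentages, where a false positive persists because the summary is cumulative, and the geometric mean neutralizing-antibody levels in SAP 3.6.3, which are meant to show what the study drugs provide.

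**Working it through.** The plan states no figure for this point, so there is none to reproduce. The check has four steps.

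**1. Is the case covered by any rule?**

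| Event after randomization | Rule for serology and neutralizing antibody |
|---|---|
| Infant receives both study products by accident | SAP Table 1: later results listed only |
| Infant receives plasma-containing blood product | None; product permitted by Protocol 4.7.1 |
| Infant receives immunoglobulin | None; not barred by Protocol 4.7.2 |

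SAP 3.1 and Appendix 2 assign every sample to a visit window, so samples taken after such a product enter the summaries. SAP 3.7.7 lists concomitant medication but does not link it to serology.

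**2. Can passive antibody meet the criterion?** Let L be the level at the previous visit (day a), Δ the days to the next visit, h the antibody half-life and r = 2^(−Δ/h). Without infection, rL remains. An amount A of passive antibody, measured at the sample, scores as exposure if rL + A ≥ 4L, so A ≥ (4 − r)L. In units of the Day 1 level, L = 2^(−(a − 1)/h). The half-life is not in the documents; 21 to 40 days is assumed.

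| Consecutive samples | r (h = 21; 40) | A needed, as a multiple of the Day 1 level (h = 21; 40) |
|---|---|---|
| Day 1 to 31 | 0.372; 0.595 | 3.63; 3.41 |
| Day 31 to 151 | 0.019; 0.125 | 1.48; 2.30 |
| Day 1 to 151 (EU schedule, Appendix 2) | 0.007; 0.074 | 3.99; 3.93 |
| Day 151 to 361 | 0.001; 0.026 | 0.03; 0.30 |

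Worked line, h = 40, Day 151 to 361: r = 2^(−210/40) = 0.0263; L = 2^(−150/40) = 0.0743; A = (4 − 0.0263) × 0.0743 = 0.295.

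The threshold is high early and low late, because maternal antibody has decayed by Day 151. Two limits apply. A is what remains when the sample is taken, so a product given soon after Day 151 will largely have gone by Day 361. The formula also ignores any assay floor, which would raise the late threshold.

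**3. Size of one false positive.** Shift = 100/n percentage points, on planned arm sizes:

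- Season 1, CLD/CHD cohort: 100/200 = 0.5 (MEDI8897); 100/100 = 1 (palivizumab).
- Season 1, all subjects: 100/600 = 0.17; 100/300 = 0.33.
- Season 2: 100/200 = 0.5 (MEDI8897/MEDI8897); 100/50 = 2 in each arm re-randomized after palivizumab.

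The denominator is the number of subjects with a result, so missing samples make the shifts larger.

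**4. Size of several.** If a fraction f of infants is misclassified and true exposure is e, observed exposure is e + (1 − e)f. Both inputs are assumptions. With e = 5%, f = 1% gives 5.95% and f = 10% gives 14.5%. With e = 20%, the same values of f give 20.8% and 28.0%.

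For neutralizing antibody, one infant whose level is raised k-fold multiplies the group geometric mean by k^(1/n). With k = 4 (assumed), 4^(1/100) = 1.014 and 4^(1/50) = 1.028, that is 1.4% and 2.8%.

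**The case against.** The best case against is that little depends on this. Serology and neutralizing antibody are exploratory, the study tests no hypothesis, and anticipated antibody use is screened out at entry. Not every recipient becomes a false positive, because step 2 shows strong dependence on timing. Use should not differ systematically between randomized arms, so the rates would tend to rise in both. All of this stands and sets the severity. It does not remove the gap, because the criterion still cannot separate donor antibody from the infant's own.

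A reader might infer more than the documents support:

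- **That the protocol contradicts itself.** An entry criterion does not conflict with later supportive care. Only blood products are expressly permitted; immunoglobulin and commercial palivizumab are left open by silence.
- **That off-study prophylaxis distorts efficacy.** Counting observed events under ITT is a usual choice. The sensitivity set in SAP 3.5.1.3 excludes subjects with missed or out-of-window active doses and, read literally, MEDI8897-arm infants who received palivizumab from any source. It does not cover immunoglobulin, or extra palivizumab on top of complete palivizumab dosing. If a share q of 1% to 10% received prophylaxis preventing a share v of 50% to 80% of events (both assumed), expected events N(1 − qv) would be 35.8 to 33.1 against 36, and 17.9 to 16.6 against 18.
- **That one infant moves a CHD exposure rate by 3 points.** This takes 1 of about 33 palivizumab infants, from 100 CHD infants at 2:1. SAP 3.6.4 plans tables by cohort, not for CHD alone.
- **That ADA results are invalid after plasma.** No mechanism for this follows from the documents, and ADA is a secondary endpoint.

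**Conclusion.** The point holds for RSV serology and neutralizing antibody only. As written, SAP 3.6.4 can count passively received polyclonal antibody as RSV exposure and keep that result at every later visit, and no rule removes the affected samples. On planned arm sizes each false positive adds 0.5 or 1 percentage point in the Season 1 CLD/CHD arms and 2 points in the two small Season 2 arms.

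The number of such infants cannot be derived: the documents give no rate of bypass surgery, transfusion or immunoglobulin use. The conclusion also assumes that donor products contain RSV antibody, and the thresholds in step 2 depend on assumed half-lives. The safety, PK, ADA and efficacy conclusions are not affected. The severity is low, but the change is worth making because it is cheap before unblinding.

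**What to change.** 1. Before unblinding for the primary analysis, flag from the recorded concomitant medication every infant who received non-study immunoglobulin, an RSV antibody or a plasma-containing product, with the date. First confirm that the eCRF distinguishes product types, such as plasma from red cells; Protocol 4.7 shows only that medication is recorded.
2. In SAP 3.2, Table 1, extend the dose-switch convention: RSV serology and neutralizing-antibody results after such a product are listed, not summarized. State that an infant who met the exposure criterion before receipt keeps that status. Alternatively, show the exposure summary in SAP 3.6.4 with and without these results, which avoids losing all late samples after one early transfusion.
3. Leave ADA results and the ITT efficacy summaries as planned. A matching RSV LRTI sensitivity summary covering both arms is optional.
4. Reconcile Protocol 4.1.3, 4.7.1 and 4.7.2 so that the position on antibody use after randomization is explicit. The clinical rule is for the sponsor to set.

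The cost is a few lines of SAP text, one flag and a check of the eCRF. The downside of listing is that some samples leave exploratory tables, probably mainly from operated CHD infants.
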